8.2.3. Biomarker Testing

Samples for biomarker testing will be collected at some or all sites participating in the study. Blood samples for biomarker testing will be drawn on the Day -1 and Day 14 visits. Proteomic biomarker testing and immunological testing will be performed on serum samples and samples containing peripheral blood mononuclear cells, respectively. Blood samples may be drawn anytime during the Day -1 visit, anytime after dosing during the Day 14 visit. Please refer to the laboratory manual for specifics of the preparation of the blood samples. No genetic biomarker testing will be performed.

Tear samples must be drawn at 10:00 ($\pm 30m$) AND at least 10 minutes prior to IOP measurement within that time window. Please refer to the study procedures manual for details of the tear collection and preparation of samples.

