2.3. Exploratory Objectives

- To evaluate changes in proteomic and immune biomarkers from Baseline

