When patients return to the clinic on Day 14 for site administration of the morning dose with assessments up to approximately 14 hours after the AM dose. The Day 14 evening dose (final dose) will be administered on-site with subsequent exit procedures performed. If EOS/ET procedures cannot occur on Day 14 (due to scheduling conflicts, site hours, etc.,) the Day 14 PM dose can be self-administered, with the patient returning within 2 days of Day 14 for EOS procedures (see Table 2).

IOP efficacy will be evaluated by Goldmann applanation tonometry. Safety/tolerability will be evaluated by review of ocular signs and symptoms through BCVA, ophthalmic assessments, ocular comfort PRO, vital signs, and other standard safety measures.

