3.5. Criteria for Study Termination

The Sponsor reserves the right to discontinue the study at any time for clinical or administrative reasons.

Figure 1: Study Design

*Day 14 (PM dose) to occur on-site with EOS procedures following. If EOS procedures cannot occur post-PM dose on Day 14 (PM dose), the patient may self-administer at home and will return for EOS/ET within 2 days.

Table 2: Schedule of Assessments

	Visit 1	Visit 2	Visit 3		Visit 4		Visit 5	Visit 5a	
If not treatment naïve must wash-out of IOP-lowering therapy prior to Day-1.	Screening / Wash-out (D-35 to -2)	Day -1	Day 1		Day 7		Day 14	EOS/ ET (D 14+2)	Day 14 – PM dose to occur on-site with EOS procedures following. Patient to self-administer PM dose if EOS procedures to occur on separate day. Procedures listed in EOS/ET are to be performed for any early terminations
Informed Consent	X								
Demographics	X								
Medical/Ophthalmic/Surgical Hx	X	X							Confirm changes from screening at Day-1
Inclusion/Exclusion	X	X	X						Specific criteria must be confirmed at Day-1 and Day 1 (pre-dose)
BCVA & Pupil Diameter	X		X		X		X	X	Screening: baseline manifest refraction included with VA Post-dose BCVA with ≥ 2 log line drop requires further assessment (repeat MR, assessment of AE, etc.)
Slit Lamp Biomicroscopy	X		X		X		X	X	Screening: includes gonioscope
Biomarker Collection - Blood		X					X		May be performed anytime during the Day -1 visit, anytime after dosing during the Day 14 visit.
Biomarker Collection - Tears		X					X		Performed at 10:00 (± 30 m) and must be performed at least 10 minutes prior to IOP measurement within time window
Intraocular Pressure (IOP)	X	S	S		S		S	X	Serial: 08:00 (± 30 m), 10:00 (± 30 m) and 16:00 (± 30 m). IOP is to be measured at the same time on visit days as Day-1.
Central Corneal Thickness	X							X	
Vital Signs	X		X		X		X	X	Performed after 5 mins of rest. Blood pressure, heart rate and respiratory rate.
Dilated Fundoscopy	X							X	
Visual Field	X							X	Results within 3 months of screening used for entry if using automated threshold visual field (24-2 or SITA Fast) and considered reliable
Safety Labs	X							X	Includes – chemistry, hematology, and urinalysis.
Pregnancy Test	X	X						X	For females of childbearing potential. Serum at Screening, urine at visits 2 and 5a.
Drug/Alcohol Screen	X	X							Testing will be repeated once prior to randomization to confirm a positive test at screening or day -1.

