7.2. Visit 2: Day-1

- Perform drug and alcohol testing (if positive, will be repeated once prior to Day 1). Patients with a confirmed positive test must be screen-failed and are not eligible for re-screening.
- Review and documentation of AEs and concomitant medication
- 08:00 ($\pm 30m$) IOP, confirm eligibility prior to performing remaining assessments
- Urine pregnancy testing for females of childbearing potential
- Blood draw and tear collection for biomarkers; blood draw may occur anytime during the visit. Tear collection must occur at 10:00 ($\pm 30m$) AND at least 10 minutes prior to IOP measurement within that time window.
- IOP at 10:00 ($\pm 30m$) and 16:00 ($\pm 30m$)
- Confirm changes from screening in medications, procedures, and medical history

7.3. Visit 3: Day 1

IOP measurements must be performed at the same time as the Day-1 time points, when possible.

- Review and documentation of AEs and concomitant medication
- Pre-dose (confirm changes from last visit)
 - BCVA & Pupil Diameter
 - Vital signs
 - Ocular Comfort PRO
 - Slit lamp
 - IOP at 08:00 ($\pm 30m$)
 - Confirmation of eligibility and randomization via IRT
- Site administration of study treatment should occur **immediately** after 08:00 IOP and IRT randomization.
- Post-dose
 - Ocular Comfort PRO: administered immediately after drop instillation up to 2 mins, 5m ($\pm 2m$), and 10m ($\pm 5m$). *If at 10 minutes, PRO rating has not returned to the visit day pre-dose value, administer every 30 minutes until pre-dose value is achieved.*
 - IOP: 10:00 ($\pm 30m$) and 16:00 ($\pm 30m$)
- Prior to the patient's departure from the clinical site the staff shall:
 - Discuss diversion prevention and IP expectations.
 - Demonstration of drop instillation provided to patient.

- Dispense study treatment kit to the patient for at home, self-administration starting with the PM dose
- AM dose should occur at 08:00, the PM dose to occur approximately 12 hours after AM dose

7.4. Visit 4: Day 7

Assessments for Day 7 are similar to Day 1. However, eligibility/randomization is not required.

- Review and documentation of AEs and concomitant medication
- Pre-dose
 - BCVA & Pupil Diameter
 - Vital signs
 - Ocular Comfort PRO
 - Slit Lamp Biomicroscopy
 - IOP at 08:00 ($\pm 30m$)
- Site administration of study treatment should occur **immediately** after 08:00 IOP
- Post-dose

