 - Ocular Comfort PRO: administered immediately after drop instillation up to 2 mins, 5m ($\pm 2m$), and 10m ($\pm 5m$). *If at 10 minutes, PRO rating has not returned to the visit day pre-dose value, administer every 30 minutes until pre-dose value is achieved.*
 - IOP: 10:00 ($\pm 30m$) and 16:00 ($\pm 30m$)
- All vials and cartons of study treatment will be returned, staff will perform vial level accountability
 - Staff will determine if doses were missed and discuss with the patient reason for missing doses (i.e., AE occurred)
- Dispense another kit of study treatment through the IRT system.
 - Discuss diversion prevention and IP expectations.
- Patient will self-administer PM dose
 - The PM dose to occur within 12 hours of AM dose

7.5. Visit 5: Day 14

Assessments for Day 14 are similar to Day 7. The visit will be longer as the last dose should be performed on-site (PM dose) with EOS procedures following. Patients will return their used and un-used IP since the Day 7 dispensation.

- Review and documentation of AEs and concomitant medication
- Pre-dose
 - BCVA& Pupil Diameter
 - Vital signs
 - Ocular Comfort PRO
 - Slit Lamp Biomicroscopy
 - IOP at 08:00 ($\pm 30m$)
- Site administration of study treatment should occur **immediately** after 08:00 IOP
- Post-dose
 - Ocular Comfort PRO: administered immediately after drop instillation up to 2 mins, 5m ($\pm 2m$), and 10m ($\pm 5m$). *If at 10 minutes, PRO rating has not returned to the visit day pre-dose value, administer every 30 minutes until pre-dose value is achieved.*
 - Blood draw and tear collection for biomarkers; blood draw may occur anytime during the visit after dosing. Tear collection must occur at 10:00 ($\pm 30m$) AND at least 10 minutes prior to IOP measurement within that time window.
 - IOP: 10:00 ($\pm 30m$) and 16:00 ($\pm 30m$)
- All vials and cartons of study treatment will be returned, staff will perform vial level accountability
 - Staff will determine if doses were missed and discuss with the patient reason for missing doses (i.e., AE occurred)
- If possible, PM dose will be administered by site staff 12 hours after the AM dose. No Ocular Comfort PRO is required.
 - Procedures for EOS will be performed after the PM dose.

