8.3.4. Intraocular Pressure

IOP measurement should be conducted after the biomicroscopy exam is completed and prior to pupil dilation, as applicable. IOP will be measured using a Goldmann applanation tonometer, using a masked-examiner method. A 2-person reading method will be used for all IOP measures wherein 1 person adjusts the dial in a masked fashion and a second person reads and records the reading. All pressure will be recorded in mmHg. Two consecutive measurements are taken in each eye and recorded as the mean of the two measurements. If the two measurements differ by >1.0 mmHg, a third measurement is performed, and the median is recorded.

As IOP measurements vary throughout the day, Day-1 will provide a baseline diurnal IOP for patients. Serial IOP measurements must be performed within time windows.

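### Biomarker blood draws are not matched by clock time between Day -1 and Day 14, so the exploratory within-arm change can carry a time-of-day component and the comparison with placebo loses precision

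*Protocol*

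**What the plan says.** The objective in 2.3 is "To evaluate changes in proteomic and immune biomarkers from Baseline". Section 10.4.4 plans descriptive summaries and change from baseline between Day -1 and Day 14. It states no test, and neither section names a comparison with placebo.

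The timing of the blood draw appears in four places, and they agree:

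- Section 8.2.3: "Blood samples may be drawn anytime during the Day -1 visit, anytime after dosing during the Day 14 visit".
- Table 2, biomarker blood row: "May be performed anytime during the Day -1 visit, anytime after dosing during the Day 14 visit".
- Section 7.2 (Day -1): "blood draw may occur anytime during the visit".
- Section 7.5 (Day 14): "blood draw may occur anytime during the visit after dosing".

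None of them sets a clock window, a match to the patient's own Day -1 time, or an interval after dosing. Section 8.2.3 points to the laboratory manual for preparing the blood samples, not for when to draw them.

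The other serial measures are treated differently. Tears, which serve the same exploratory purpose at the same two visits, are taken at 10:00 (±30 minutes) both times. Table 2 asks for IOP at the same time of day as on Day -1, and 8.3.4 gives the background: "As IOP measurements vary throughout the day".

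**The concern.** A change from baseline is easiest to read when both samples are taken under the same conditions apart from treatment. Here clock time can differ between the two samples, and the Day 14 sample can fall anywhere from just after the morning dose to late in the visit. Section 3.1 allows Day 14 "assessments up to approximately 14 hours after the AM dose" when the patient stays for the evening dose on site.

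If a serum protein or a mononuclear-cell measure varies over the day, part of that variation enters the within-arm change. In the active arms the change also averages over whatever post-dose times the sites happened to choose. Extra spread from unmatched times makes the comparison of each dose with placebo less precise. Groups are planned at 18, and 8.2.3 allows the samples to come from only some sites, so fewer patients may contribute. This is a stated rule, not a detail left open for the analysis plan, and no analysis can recreate matched samples once the blood has been drawn.

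**Working it through.** The protocol gives no biomarker figure to reproduce. The check sets out what the timing rule permits and then illustrates its effect.

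**Inputs from the protocol**

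- Day -1 (7.2): IOP at 08:00, 10:00 and 16:00, each ±30 minutes, so visit hours of about 07:30 to 16:30. The first listed IOP entry requires "IOP, confirm eligibility prior to performing remaining assessments", so blood follows that reading.
- Day 14 (7.5): dosing immediately after the 08:00 IOP, last serial IOP at 16:00 (±30 minutes). The visit may run to about 08:00 + 14 h = 22:00 (3.1).

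**Permitted timing**

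| | Day 14 ends 16:30 | Day 14 runs to 22:00 |
|---|---|---|
| Time since AM dose | 0 to 8.5 h | 0 to 14 h |
| Smallest gap (Day 14 minus Day -1) | 8.0 − 16.5 = −8.5 h | −8.5 h |
| Largest gap | 16.5 − 7.5 = +9.0 h | 22.0 − 7.5 = +14.5 h |
| Mean gap, uniform draw times | 12.25 − 12.0 = +0.25 h | 15.0 − 12.0 = +3.0 h |

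For tears the largest gap is 10:30 − 09:30 = 1 h.

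**Illustration of the effect**

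These assumptions are not in the documents: uniform and independent draw times in the windows above; a 24-hour cosine rhythm peaking at 08:00 with amplitude A, in units of the SD of the change when times are matched; 18 patients per arm; no drug effect.

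The mean of the rhythm over a window from a to b is

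A × (24/2π)/(b − a) × [sin(2π(b − 8)/24) − sin(2π(a − 8)/24)].

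For A = 1:

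- Day -1 (07:30 to 16:30): 3.82/9 × (0.793 + 0.131) = 0.392
- Day 14 (08:00 to 16:30): 3.82/8.5 × 0.793 = 0.357, so the within-arm shift is 0.357 − 0.392 = −0.04 SD
- Day 14 (08:00 to 22:00): 3.82/14 × (−0.5) = −0.136, so the within-arm shift is −0.136 − 0.392 = −0.53 SD

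A simulation of 20,000 trials per setting agrees:

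| Day 14 window | A | Within-arm mean change (SD) | Within-arm false-positive rate | Variance ratio | Active minus placebo (SD) | Between-arm false-positive rate |
|---|---|---|---|---|---|---|
| to 16:30 | 0.25 | −0.01 | 5% | 1.04 | 0.00 | 5% |
| to 16:30 | 0.5 | −0.02 | 5% | 1.14 | 0.00 | 5% |
| to 16:30 | 1.0 | −0.04 | 5% | 1.53 | 0.00 | 5% |
| to 22:00 | 0.25 | −0.13 | 8% | 1.05 | 0.00 | 5% |
| to 22:00 | 0.5 | −0.27 | 16% | 1.20 | 0.00 | 5% |
| to 22:00 | 1.0 | −0.53 | 35% | 1.81 | 0.00 | 5% |

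The false-positive rates are for an illustrative 5% t-test, since 10.4.4 plans none. At A = 1.0 the standard error of a between-arm difference grows by √1.53 = 1.24 or √1.81 = 1.35. At A = 0.5 the factors are √1.14 = 1.07 and √1.20 = 1.10.

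**What matching would leave**

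The rhythm changes by at most 2πA/24 = 0.262A per hour. With Day 14 times uniform within ±1 h of the Day -1 time, the added variance is at most (0.262A)²/3 = 0.023A². The variance ratio at A = 1.0 is then at most about 1.02.

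**The case against.** A reader might infer that time of day is confounded with the drug effect. The documents do not support that for the comparison that identifies a drug effect. Allocation is 1:1:1 with a placebo arm, patients and sites are masked (3.2.1), and all arms follow the same sampling rule. Time of day therefore cancels in expectation between active and placebo, as the table shows. That part of the objection stands in full.

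A reader might also take a gap of about 14 hours as typical. It is an extreme. It needs a draw at the very start of Day -1 and another after the evening dose on Day 14. Section 7 asks for assessments in the listed order, and both 7.2 and 7.5 list blood together with tears, between the 08:00 and 10:00 IOP readings. Followed as listed, both draws fall in the same part of the morning, and the on-site evening dose is itself conditional. This stands as a statement of what is likely. It does not remove the permission, because four places expressly release the blood draw from a set time.

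Three further points have weight. The documents do not show that these markers vary over the day or with hours since dose, and the remark in 8.3.4 concerns IOP only. The endpoint is exploratory and descriptive, with no test or power claim. Section 8.2 refers to a laboratory manual for sample collection, which may narrow the timing, although the protocol itself would still permit any draw time. Finally, the 10:00 slot already holds tears and an IOP reading that enters the primary endpoint, and the Synopsis drops a patient's Day 14 mean if any time point is missing. Moving blood into that slot would therefore carry a cost, which is a reason to match on the patient's own draw time instead.

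**Conclusion.** The point holds as a minor one. The blood draw lacks the clock matching that the protocol gives to tears and IOP. The within-arm change, the only change measure that 10.4.4 names, can thus include a time-of-day component and averages over an undefined time since dose. The active-versus-placebo difference is not biased by time of day, but it is less precise, and the post-dose time it represents is not defined.

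The size depends on two things that the documents do not give: the rhythm of each marker and the draw times that sites choose. Under the stated assumptions, within-arm bias is negligible (at most 0.04 SD) if draws end by 16:30, with variance raised by 4% to 53% for amplitudes of 0.25 to 1.0 SD. It reaches 0.13 to 0.53 SD, with variance raised by 5% to 81%, only if Day 14 draws spread evenly to 22:00. With no rhythm there is no time-of-day effect. The primary and secondary endpoints are untouched.

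**What to change.** In 7.2, 7.5, 8.2.3 and Table 2, replace the open timing of the blood draw with the following:

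- Take the Day 14 sample after the morning dose and before the evening dose, within about ±60 minutes of that patient's Day -1 draw time.
- Record the clock time of both draws, and the time since dose on Day 14.
- Do not let the draw displace the 10:00 tear collection or any IOP reading.

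In 10.4.4, state that biomarker changes will be interpreted against placebo, not from within-arm change alone.

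Day -1 draws taken by 16:30 would put the matched Day 14 draw no later than 17:30, before an evening dose at about 20:00. A very early Day -1 draw leaves little room after dosing on Day 14, so sites should choose a Day -1 time that they can repeat.

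The cost is protocol wording, two recorded times and less scheduling freedom for sites. No extra sample or visit is needed.

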8.3. Ophthalmic Assessments

When applicable, assessments requiring dilation should occur at the end of the visit. Detailed instructions can be found within the study procedure manual.

8.3.1. Manifest Refraction

Conducted at the screening visit for distance at 4M using the clinic's standard practices for the right (OD) and left (OS). The manifest refraction measurements from screening will be used for subsequent BCVAs.

8.3.2. Visual Acuity

Best Correct Visual Acuity (BCVA) will be measured at time points noted in [Table 2](#). It is recommended that the ETDRS Chart 1 be used for testing the right eye and the Chart 2 be used for testing the left eye. BCVA testing should precede slit lamp examination, intraocular pressure measurement, the administration of topical anesthetic agents or any examination requiring contact with the eye.

Visual Acuity will be assessed monocularly in both eyes, testing the right eye first and then the left eye. The patient should be positioned according to the elevation of the chart (either seated or standing) so that the chart is at a comfortable viewing angle. The patient should attempt to read each letter, line-by-line, left to right, beginning with line 1 at the top of the chart. The patient should be told that the chart has letters only, no numbers. If the patient reads a number, they should be reminded that the chart contains no numbers, and the examiner should then request a letter instead of the number. The patient should be asked to read slowly, about 1 letter per second, to achieve the best identification of each letter. The patient is not to proceed to the next letter until they have given a definite response. If the patient changes a response before he has read aloud the next letter, then the change must be accepted.

Maximum effort should be made to identify each letter on the chart; the patient should be encouraged to guess. When it becomes evident that no further meaningful readings can be made, the examiner should stop the test. The number of letters missed or read incorrectly should be noted.

In order to provide standardized and well-controlled assessments of visual acuity during the study, the same lighting conditions must be used consistently throughout the study.

Calculations: $\text{LogMAR VA} = \text{Baseline value} + (n \times 0.02)$

- where: the baseline value is the LogMAR number of the last line read (at least 1 letter read correctly in this line), and “n” is the total number of letters missed up to and including the last line read, and “0.02” is the value for each letter.

8.3.2.1. Losses in Visual Acuity

If a patient loses ≥ 2 lines (defined as 10 or more letters) in BCVA in comparison to the Day 1 (pre-dose) BCVA measurement, this will warrant further assessment to determine the reason for the loss (i.e., repeat manifest refraction and/or other ophthalmic assessments). If a repeat manifest refraction is performed, it should be conducted in the corresponding eye and assessed for safety by the Investigator. It is the Investigator's discretion to perform the repeat manifest refraction in each eye.

The assessment(s) performed to assess the safety and reason for visual acuity losses must have corresponding documentation of actions taken, noted in the source.

8.3.3. Pupil Diameter

Pupil diameter will be assessed by pupillometer following BCVA assessment as per time points delineated in Table 2. Pupil Diameter will be conducted using the same logMAR chart as the distant target for the uncovered eye not being tested.

8.3.4. Intraocular Pressure

IOP measurement should be conducted after the biomicroscopy exam is completed and prior to pupil dilation, as applicable. IOP will be measured using a Goldmann applanation tonometer, using a masked-examiner method. A 2-person reading method will be used for all IOP measures wherein 1 person adjusts the dial in a masked fashion and a second person reads and records the reading. All pressure will be recorded in mmHg. Two consecutive measurements are taken in each eye and recorded as the mean of the two measurements. If the two measurements differ by >1.0 mmHg, a third measurement is performed, and the median is recorded.

As IOP measurements vary throughout the day, Day-1 will provide a baseline diurnal IOP for patients. Serial IOP measurements must be performed within time windows.

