2.1.3. Safety Endpoints

- Change from baseline in vital signs including heart rate and blood pressure
- Change from baseline in safety labs
- Adverse Events (overall, ocular, and non-ocular)
- Change from baseline in ophthalmic assessments – slit lamp biomicroscopy, dilated fundus exam, BCVA, pupil diameter, visual field and pachymetry

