4.3. Withdrawal Criteria

4.3.1. Screen Failures

Screen failures are defined as patients who consent to participate in the clinical study but do not meet inclusion/exclusion criteria. A minimal set of screen failure information is required to ensure transparent reporting of screen failure patients to meet the Consolidated Standards of Reporting Trials publishing requirements and to respond to queries from regulatory authorities. Minimal information includes screen failure reason, eligibility criteria, and any serious adverse event (SAE).

If a patient is a screen failure due to wash-out from ocular procedures listed in exclusion criteria #7, the Investigator may contact the Medical Monitor and discuss the potential for re-screening in advance of wash-out completion. If the Medical Monitor agrees, the Investigator may schedule a re-screening upon completion of wash-out and file documentation of discussion within their site files.

All other individuals who do not meet the criteria for participation in this study (screen failure) will not be re-screened.

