7. STUDY VISITS

Where possible, assessments should be conducted in order of least invasive to most invasive.

All ophthalmic assessments will be performed in each eye. Assessments within a visit should occur in the order noted below. Additional instructions on study assessments will be provided within the study procedure manual.

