7.1. Visit 1: Screening (Day -35 to Day -2)

Patients will be provided with an ICF and given time to review study information and ask any questions prior to signing. As part of the consent discussion, investigator/designee should discuss diversion prevention and expectations regarding IP accountability processes.

After the consent form is signed, with a copy of the signed ICF provided to the patient, the following assessments will be carried out as follows:

- Perform drug and alcohol testing (if positive, will be repeated once prior to Day -1). Patients with a confirmed positive test must be screen-failed and are not eligible for re-screening.
- Review/documentation of
 - Demographic information
 - Medical, ophthalmic, and surgical history
 - Prior and concurrent medications/therapies, planned ocular procedures
 - Childbearing potential, methods of birth control if of childbearing potential
- Baseline Manifest Refraction, BCVA and Pupil Diameter
- Slit lamp biomicroscopy, includes gonioscope to assess angle closure and lens assessment
- IOP
- Pachymeter to measure central corneal thickness
- Vital signs
- Visual field (if no results within 3 months of screening, meeting testing requirements)
- Dilated Fundus exam
- Labs
 - Chemistry, hematology, and urinalysis
 - Serum pregnancy tests for females of childbearing potential
- Review/documentation of AEs, assess eligibility
- If treatment naïve, upon confirmation of eligibility (i.e., assessment of screening labs) schedule Day-1. Otherwise begin wash-out as detailed in [5.1.3](#).

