7.6. Visit 5a: EOS/ET (Day 14+ 2 Days)

EOS procedures will be performed after the final dose of IP has been administered. If the EOS procedures cannot occur after the last dose, the Day 14 PM dose can be self-administered with the patient returning within 2 days for the EOS procedures.

- Review and documentation of AEs and concomitant medication
- BCVA and Pupil Diameter
- Slit lamp biomicroscopy and lens assessment
- IOP
- Pachymeter for central corneal thickness measurement
- Vital signs
- Dilated Fundus exam
- Visual field
- Labs
 - Chemistry, hematology, and urinalysis
 - Urine pregnancy tests for females of childbearing potential
- *All vials and cartons of study treatment will be returned, staff will perform vial level accountability*
 - *Staff will determine if doses were missed and discuss with the patient reason for missing doses (i.e., AE occurred). Required if visit is not occurring on Day 14.*

Procedures listed within this visit should be performed if a patient early terminates from the study.

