8.3.5. Central Corneal Thickness

Central corneal thickness measurements of each eye will be made using an ultrasonic pachymeter. Contact pachymetry will be performed after IOP measurement.

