8.3.6. Slit Lamp Biomicroscopy

A biomicroscopy examination will be performed without pupil dilation using a slit lamp and magnification consistent with standard clinical practice. The exam will include evaluation of patients' lids, cornea, conjunctiva, anterior chamber, and iris/pupils.

Screening will include a gonioscope to assess the angle closure. At Screening and EOS/ET, a lens assessment will be collected through a dilated pupil using the slit lamp biomicroscope. Findings will be evaluated for the presence and severity of nuclear, cortical, and posterior subcapsular lens opacities.

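### At Screening the protocol places gonioscopy ahead of the entry IOP and the only baseline corneal thickness; listing it after both is a free, minor improvement

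*Protocol*

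**What the plan says.** Five places in the protocol bear on the Screening order.

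- Section 7 asks that visit assessments follow the sequence listed, and also says: "Where possible, assessments should be conducted in order of least invasive to most invasive".
- Section 7.1 lists, in this order, refraction with BCVA and pupil diameter; "Slit lamp biomicroscopy, includes gonioscope to assess angle closure and lens assessment"; IOP; and pachymetry. The dilated fundus exam comes later.
- Section 8.3.4 places IOP relative to the slit lamp: "IOP measurement should be conducted after the biomicroscopy exam is completed and prior to pupil dilation, as applicable".
- Section 8.3.6 describes an undilated slit-lamp exam, then adds: "Screening will include a gonioscope to assess the angle closure". It also adds a lens assessment through a dilated pupil at Screening and EOS/ET. The slit-lamp row of Table 2 likewise puts the gonioscope at Screening only.
- Section 8.3.5 says: "Contact pachymetry will be performed after IOP measurement".

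At EOS/ET, 7.6 lists slit lamp with lens assessment, IOP, then "Pachymeter for central corneal thickness measurement". No gonioscopy is listed.

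The Screening readings are used as follows. Inclusion 3b requires a Screening IOP of 21 to 36 mmHg in each eye for treatment-naive patients. Exclusion 1 sets the 36 mmHg upper limit for all. Inclusion 4 requires a corneal thickness of 480 to 620 micrometres in each eye. Section 2.1.3 names change from baseline in "dilated fundus exam, BCVA, pupil diameter, visual field and pachymetry" among the safety endpoints.

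**The concern.** Gonioscopy is taken here to be a corneal-contact examination. That is its ordinary nature, but the protocol does not say so. On that premise, a contact examination comes before two entry readings, although nothing requires it to come first. Section 8.3.5 shows that the authors had such effects in mind, since it holds contact pachymetry back until IOP has been read. The same logic was not applied to gonioscopy.

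Two uses of the readings are exposed in principle. The first is entry. A patient who fails on a Screening value generally gets no second attempt: "All other individuals who do not meet the criteria for participation in this study (screen failure) will not be re-screened". The exception covers only wash-out from the ocular procedures in exclusion 7. The second is the pachymetry safety endpoint. Its baseline reading follows gonioscopy and its follow-up reading does not, so the two are taken under different conditions.

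**Working it through.** There is no plan figure to reproduce, so the check sets the sections side by side.

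**Step 1: the order at each visit as written.**

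| | Screening (7.1) | EOS/ET (7.6) |
|---|---|---|
| Slit lamp | with gonioscopy and lens assessment | with lens assessment |
| Next | IOP | IOP |
| Next | pachymetry | pachymetry |

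Sections 8.3.4 to 8.3.6 and Table 2 agree with this layout. IOP follows a completed slit-lamp exam, gonioscopy belongs to that exam at Screening, and pachymetry follows IOP.

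**Step 2: can the Screening slit-lamp line be run as one block?** No. The lens assessment in that line needs a dilated pupil (8.3.6), IOP must precede dilation (8.3.4), and 8.3 sends dilated assessments to the end of the visit. The lens assessment must therefore come after IOP. Once the line is split, the protocol does not say on which side of IOP gonioscopy falls.

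**Step 3: which readings depend on the order?** Table 2 schedules corneal thickness only at Screening and EOS/ET. Section 10.4.1 defines baseline as the last value before treatment starts, so Screening corneal thickness is the only possible baseline. Inclusion 3c takes its 08:00 IOP readings on Day -1 and Day 1, when no gonioscopy is scheduled. The diurnal baseline and the Day 14 primary endpoint also come from days without it.

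**Step 4: how would a shift travel?** Let S and E be the Screening and EOS corneal thickness, and let x be any average effect of gonioscopy on S, of unknown size and sign.

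- Recorded change in an arm: E − (S + x) = (E − S) − x. The arm's mean change moves by −x.
- Active minus placebo: (change in active − x) − (change in placebo − x) = change in active − change in placebo. The shift cancels.

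The cancellation holds because Screening precedes randomization and its order is common to all arms. Only the within-arm change and shift summaries of 10.4.5 would carry x.

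**Step 5: is gonioscopy the only difference between the two thickness readings?** That depends on when EOS takes place. If it is on Day 14, pachymetry follows tonometry at 08:00, 10:00 and 16:00 plus the EOS IOP, that is 3 + 1 = 4 sessions against 1 at Screening. It also follows two drop instillations and, where performed, tear collection. If EOS is a separate visit, one tonometry session precedes pachymetry that day, as at Screening, and gonioscopy is then the contact examination that differs.

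**The case against.** The strongest reply is that the 7.1 line is a list of components and not a sequence. Step 2 shows that it cannot be followed literally. The exam that 8.3.4 refers to may be only the undilated one described first in 8.3.6. The where-possible sentence in Section 7 would then let a site do gonioscopy later, and a procedure manual that is not at hand may settle the matter. This has force, but it leaves the protocol open to two readings across up to six centers, and its listed order still points to gonioscopy first.

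Three further objections stand.

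- Sections 8.3.2 and 8.3.5 are not breached. BCVA is listed before the slit lamp, and pachymetry after IOP. Only the general Section 7 sentence and the reasoning behind 8.3.5 are at odds with the order.
- The harm is not quantified. The protocol gives no size, direction or duration for an effect of gonioscopy on IOP or corneal thickness.
- Moving gonioscopy would not make the two thickness readings fully comparable, as Step 5 shows.

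A reader might go further and infer that a stated share of eligible treatment-naive patients would be turned away at the 21 mmHg floor. The documents do not support any such percentage. It would need an assumed mean, spread, shift and direction for Screening IOP, and zero effect is among the possibilities. It would also have to allow for patients who would fail the later 08:00 readings anyway.

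**Conclusion.** The point holds as a small, free improvement. As written, gonioscopy precedes the Screening IOP and the Screening corneal thickness, and has no counterpart before the EOS corneal thickness. What could be affected is limited to entry on the Screening values and the descriptive within-arm change in corneal thickness. The size is unknown and may be nil.

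It would be wrong to infer a threat to the efficacy result. The Day -1 and Day 1 eligibility readings, the diurnal baseline, the primary endpoint and the contrasts between arms are all unaffected. The conclusion rests on two things: the premise that gonioscopy touches the cornea, and reading the listed order as Section 7 asks.

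**What to change.** In 7.1, 8.3.4 and 8.3.6, separate the undilated slit-lamp exam from gonioscopy and from the dilated lens assessment. List the Screening sequence as slit lamp, IOP, pachymetry, gonioscopy, then the dilated assessments. In 8.3.4, say that IOP follows the undilated slit-lamp exam. The visual field stays ahead of dilation, as 8.3.8 requires. Section 7.6 also joins the lens assessment to the slit lamp ahead of IOP, so the same split there keeps the two visits parallel.

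The cost is a few lines of text, with no added procedure, visit or staff. The change also removes the conflict over the dilated lens assessment. It takes away one avoidable difference between the Screening and EOS corneal thickness, but it leaves the repeated tonometry and dosing that precede a same-day EOS reading.
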